7.5 Trial specific preventive measures

Treatment as usual will be provided to the participants. We did not fix any restriction regarding diet, and/or medication. Medication and stressful event will be monitored and described. The study aims to assess the feasibility of such study in natural settings, thus this event will happen in natural clinical time-course. We did not see any obstacle for our study objectives related to concomitant treatment.

7.6 Concomitant Interventions (treatments)

The treatment usually provided to mothers having a preterm infant will be provided to the participant. No specific intervention on stress and anxiety or HRV is usually provided at the maternity ward of CHUV. All other treatments that participants might follow will be documented.

7.7 Medical Device Accountability

Standard procedure for accurate records and storage will be applied.

[figure not shown]
7.8 Return or Destruction of Medical Device

Return or destruction of the medical devices are according to standard procedures and mentioning this in the protocol is enough (no details needed).

8. STUDY ASSESSMENTS

8.1 Study flow chart(s) / table of study procedures and assessments

Study flow chart:

8.2 Assessments of outcomes

8.2.1 Assessment of primary outcome

Feasibility will be assessed through the number of eligible participants during a month, the ratio of acceptance to participate, compliance with study protocol (number and duration of sessions, fulfilling study questionnaires) and the ratio of drop out. Satisfaction will be measured through a questionnaire (see appendix).

8.2.2 Assessment of secondary outcomes

HRV will be monitored on an electrocardiogram (ECG) for 5 min at rest with the Nexus-4 product from Mindmedia with a standard measurement procedure (sensor at finger). The root-mean square differences of successive R-R intervals (RMSDD) as well as High Frequency (HF) will be used as measures to assess HRV level before and after participation in the HRVB program.

Stress, anxiety and depression symptoms will be measured by self-reports questionnaires (see appendix):

- Perceived stress will be measured on the Perceived Stress Scale (PSS).
- Post-traumatic stress disorder symptoms will be assessed with the Post-traumatic symptoms checklist 5 (PCL-5).
- Anxiety symptoms will be assessed with the State and Trait Anxiety Inventory (STAI).
- Depression symptoms will be assessed with the Beck Depression Inventory (BDI).

8.2.3 Assessment of safety outcomes

Adverse events will be monitored during the training phase. The participant will keep a diary marking any negative events related to the HRVB program. As the program consists of a simple breathing technique, the risk that an adverse event would occur is low. At each session (before the HRVB program and after one week), the trainer will discuss with the participant adverse events that might have occurred. The participant will also have the opportunity to report adverse events by responding to the daily program reminder that she will receive by text message.

Tolerability of the HRVB protocol will be assessed at the end of the study by a qualitative interview.

8.2.4 Assessments in participants who prematurely stop the study

If a participant drops out from the study, an interview will be done to examine the reason of consent withdrawal if the participant agreed to explain her withdrew from the study. The data acquired within the study will be described in the grant proposal.

8.3 Procedures at each visit

8.3.1 Information / consent visit

The participants who fulfill inclusion criteria (without presenting exclusion criteria) will be informed orally about the study by [name] and will receive written information. The next day, they will be asked if they have any question about the study and if they agree to participate, written informed consent will be collected.

8.3.2 Pre-intervention assessment

The baseline assessment of HRV will take place at the hospital in a quiet room. Pre-intervention reports on stress, anxiety and depression will be collected with the instruments outlined in section 9.2.2.

8.3.3 HRVB training

In order to familiarize participants with the HRVB program and its apparatus as well as to assess each participant's individual resonance frequency (i.e., breathing rhythm), two training sessions will be provided: one prior to the beginning of the HRVB program (at hospital) and one after one week of HRVB program (either at the hospital or at the participant's home if she has been discharged from the hospital). The second training session aims to optimize adherence to the HRVB program and to reassess participant's resonance frequency.

9.3.5 Post-intervention visit

After two weeks of performing the HRVB program (\pm 3 days), post-intervention assessment will take place (either at the hospital or at the participant's home if she has been discharged from the hospital). Additionally, a satisfaction questionnaire has to be filled out and a debriefing interview will be conducted in order to discuss the acceptability of the protocol.

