KlinV	Verordnung über klinische Versuche in der Humanforschung (in English: ClinO, in French OClin)
LRH	Loi fédérale relative à la recherche sur l'être humain
MD	Medical Device
OClin	Ordonnance sur les essais cliniques dans le cadre de la recherche sur l'être humain (in German : KlinV, in English : ClinO)
PI	Principal Investigator
RMSDD	Root-mean square differences of successive R-R intervals
RSA	Respiratory sinus arrhythmia

STUDY SCHEDULE

Study Periods	Screening	Treatment, Intervention Period		
		Pre	Middle	Post
Visit				
Time in days postnatal	3 ± 2	7	14 ± 3	21 ± 3
Patient Information and Informed Consent	x			
Demographics	x			
Medical History	x			
In- /Exclusion Criteria	x	x		
Medical Device		x	x	x
Primary outcomes: acceptability of the protocol, acceptability of the intervention, compliance, satisfaction with the intervention.				x
Secondary outcomes: heart rate variability, perceived stress, anxiety, depression.		x		x
Concomitant Therapy		x	x	x
Adverse Events		x	x	x

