4. STUDY OUTCOMES

4.1 Primary Outcome

Feasibility of the study will be assessed through the number of eligible patients, the rate of study participation acceptance and the rate of drop out. Moreover, satisfaction will be rated on a self-report questionnaire.

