7.4 Data Collection and Follow-up for withdrawn participants

The participants who withdraw their consent or who do not comply with the HRVB program will be considered as dropouts. Intention-to-treat descriptive analyses will be done on baseline information as well as quantifying the training period (if any). All data acquired during the study will be analyzed.

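### Satisfaction, acceptability and interview-based tolerability have no planned collection from mothers who stop early, so these results will describe mainly those who stay and may be overstated

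*Combined protocol and SAP*

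**What the plan says.** The primary objective (3.2) is acceptability of the protocol and the intervention, and satisfaction with the intervention. Section 4.1 gives the measures as follows: "Feasibility of the study will be assessed through the number of eligible patients, the rate of study participation acceptance and the rate of drop out". It then adds satisfaction by self-report questionnaire. Section 8.2.1 adds "compliance with study protocol (number and duration of sessions, fulfilling study questionnaires) and the ratio of drop out". Tolerability is a safety outcome (4.3).

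Timing is as follows.

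- **Satisfaction and acceptability debriefing:** section 9.3.5, at the post-intervention visit: "a satisfaction questionnaire has to be filled out and a debriefing interview will be conducted". The interview is about how acceptable the protocol was. The study schedule has a row headed "Primary outcomes: acceptability of the protocol, acceptability of the intervention, compliance, satisfaction with the intervention" with a single mark, which appears to sit in the Post column.
- **Tolerability:** section 8.2.3: "Tolerability of the HRVB protocol will be assessed at the end of the study by a qualitative interview". Negative events are also gathered during training, through the diary, the trainer sessions and text replies.
- **Mothers who stop:** section 8.2.4: "an interview will be done to examine the reason of consent withdrawal", provided the mother agrees to explain.
- **Who counts as a dropout:** section 7.4: "The participants who withdraw their consent or who do not comply with the HRVB program will be considered as dropouts".

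On analysis, 10.4 reports acceptability and satisfaction descriptively and names no denominator. Section 10.4.1 keeps drop-out data for description only, and 10.5 analyses completers only. Section 7.4 promises descriptive intention-to-treat summaries of baseline and training data, and the use of everything acquired. Section 6.3 first excludes mothers below the minimum training and then says that their data will be analysed.

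**The concern.** A mother who finds the programme burdensome or unhelpful is a natural candidate to stop. Her opinion is then the one the plan has no instrument to record. The drop-out rate will show that she left, and the exit interview may show why, but neither gives a satisfaction rating or an account of tolerability comparable with those of the mothers who stayed.

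The study is meant to inform a larger project (2.3). A favourable satisfaction figure based only on mothers who reached the last visit could be carried forward as if it described everyone enrolled. With 10 participants, one or two missing ratings change the picture visibly.

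**Working it through.** **1. What each group is asked**

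| | Reaches post visit | Withdraws consent | Non-compliant, counted as dropout under 7.4 |
|---|---|---|---|
| Drop-out and compliance data | yes | yes | yes |
| Negative events during training | yes | until she stops | while she takes part |
| Satisfaction questionnaire | yes (9.3.5) | not planned | only if she attends the post visit |
| Acceptability debriefing | yes (9.3.5) | not planned | only if she attends the post visit |
| End-of-study tolerability interview | yes (8.2.3) | not planned | only if she is seen at the end of the study |
| Exit interview on the reason | not applicable | if she agrees (8.2.4) | unclear: 8.2.4 opens with drop-out but asks about consent withdrawal |

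The schedule is weak evidence by itself. The table is flattened in the text available, and the same row lists compliance, which accrues daily. The finding rests on 9.3.5, 8.2.3 and 8.2.4.

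**2. Inputs for size**

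The plan gives 10 participants. It states no drop-out rate and no satisfaction rate, and the text available gives no cut-off for calling a mother satisfied; the questionnaire is in an appendix not available here. So there is no figure of the plan's own to reproduce on this point, and what follows is illustration under stated assumptions.

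**3. Bounds over all enrolled**

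Let N = 10, m = mothers without a rating, and k = satisfied among the N − m who respond. The responder figure is k/(N − m). Over all enrolled, the true figure lies between k/N (none of the missing satisfied) and (k + m)/N (all of them satisfied). The width is m/N, that is, 10 points per missing mother.

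| m | Responders, all satisfied | Bounds over 10 |
|---|---|---|
| 1 | 9/9 = 100% | 90–100% |
| 2 | 8/8 = 100% | 80–100% |
| 3 | 7/7 = 100% | 70–100% |
| 4 | 6/6 = 100% | 60–100% |

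Sampling error comes on top. Exact (Clopper–Pearson) 95% intervals are 63–100% for 8/8 against 44–97% for 8/10, and 59–100% for 7/7 against 35–93% for 7/10.

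**4. Expected overstatement**

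Let d = drop-out share, s_c = satisfied share among completers, and s_l = satisfied share among leavers. The all-enrolled value is (1 − d)·s_c + d·s_l. The completer figure exceeds it by

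s_c − [(1 − d)·s_c + d·s_l] = d·(s_c − s_l).

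Take s_c = 0.90 as an assumption:

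| s_l | d = 0.20 | d = 0.30 |
|---|---|---|
| 0.90 | 0.20 × 0 = 0 points | 0.30 × 0 = 0 points |
| 0.50 | 0.20 × 0.40 = 8 points | 0.30 × 0.40 = 12 points |
| 0 | 0.20 × 0.90 = 18 points | 0.30 × 0.90 = 27 points |

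The sign would reverse if leavers were more satisfied than completers. Without their ratings the plan cannot tell which case applies.

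**The case against.** The strongest reply is that the plan does not lose sight of these mothers. Drop-out and compliance are themselves primary measures, so every departure counts openly against feasibility. Dropouts' baseline and training data are summarised (7.4), negative events are collected throughout training (8.2.3), and an exit interview is planned (8.2.4). Satisfaction is only described, and 10.4.1 allows drop-out data for description.

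Most of this stands, and it rules out several stronger readings that a reader might infer:

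- **Leavers contribute nothing.** Not supported: they supply drop-out, compliance, baseline, training and negative-event data.
- **The primary outcome as a whole is biased upward.** Not supported: the numbers eligible, accepting, dropping out and complying are untouched. Only satisfaction and the acceptability debriefing are exposed. Tolerability is a safety outcome and cannot bias the primary one.
- **Non-compliers are shut out of the ratings.** Not supported: 9.3.5 sets no compliance threshold and allows a home visit.
- **The overstatement is 20 to 30 points.** That is the worst case at 2 or 3 losses out of 10, with every completer satisfied and no leaver satisfied. Nothing in the documents fixes those values.

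What the reply does not answer is narrower. Counting departures does not measure satisfaction. The exit interview depends on the mother's agreement, is framed around the reason for withdrawal and names no satisfaction or tolerability measure. If a non-complier does complete the questionnaire, 6.3, 7.4, 10.4.1 and 10.5 disagree on whether her rating is reported.

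**Conclusion.** The point holds in limited form. As written, satisfaction, acceptability and interview-based tolerability will describe mainly mothers who stay, and they may be overstated. Upward bias is plausible but not demonstrated. Its size is 0 to 18 points at 20% drop-out and 0 to 27 points at 30%, on the assumptions that 90% of completers are satisfied and that leavers are no more satisfied than completers. It is zero if the two groups are equally satisfied. The one part that follows from the enrolled number alone is that each missing rating widens the all-enrolled bounds by 10 points.

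This does not undermine the study's feasibility counts. It is a cheap improvement to one named component of the primary outcome and to the safety outcome.

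**What to change.** - **Section 8.2.4:** at the exit contact already planned, offer the same satisfaction questionnaire together with the acceptability and tolerability questions. State that this contact, or the post-intervention visit, is also offered to mothers counted as dropouts for non-compliance under 7.4. Update the study schedule to match.
- **Section 10.4:** report satisfaction and tolerability with the number of mothers providing data out of the number enrolled. For satisfaction, add a bound that counts mothers without data as not satisfied.
- **Sections 6.3, 7.4, 10.4.1 and 10.5:** reconcile them so that ratings from dropouts and non-compliers are included in this descriptive report.

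The cost is a few sentences of protocol wording and a slightly longer exit contact for a small number of mothers. Some will decline, so the gap may shrink without closing; that is why the denominator and the bound are needed as well.

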9. SAFETY

9.1 Medical Device Category A studies

9.1.1 Definition and Assessment of safety related events

Health hazards which may occur during the participation in the study and that require measures will be documented.

Participants at the beginning of the study will be hospitalized, thus, the likelihood of detecting additional health hazards from the study is low.

9.1.2 Reporting of Safety related events

Severe safety related events refer to (a) incident that necessitate inpatient stay or a prolongation of the inpatient stay which was not planned in the research protocol; (b) lead to severe or chronic handicap or invalidity; (c) caused decease or life threatening; (d) to congenital anomaly or malformation. Such event will be reported to the Sponsor-Investigator within 24 hours upon discovery. The local Ethics Committee will be informed within 15 days. At this time, we did not see any other safety related events that might be documented here.

9.1.3 Safety events detected by chance

Any abnormal ECG patterns detected by chance (no specific assessment by a cardiologist of the ECG measurement) that require medical monitoring and/or intervention will be reported. In such case, an appointment with a cardiologist will be offered to the participant.

10. STATISTICAL METHODS

10.1 Hypothesis

H0: The HRVB program will not show to be feasible and efficient in terms of increasing HRV and reducing stress, anxiety and/or depression.

H1: The HRVB program will show to be feasible and efficient in terms of increasing HRV and reducing stress, anxiety and/or depression.

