4.2 Secondary Outcomes

HRV (i.e., root-mean square differences of successive R-R intervals), perceived stress, and mental health (anxiety, depression, PTSD).

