10.4 Planned Analyses

Acceptability of the study protocol and intervention as well as satisfaction will be reported descriptively. The inferential analyses will consist in comparing variables (HRV and mental health symptoms) from baseline to post-HRVB intervention using non-parametric Kruskall-Wallis tests. By convention, statistical significance will be set at .05.

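### Section 10.1 joins feasibility and efficacy in one H0/H1 that the section 10.4 analyses cannot decide: feasibility is only described, and separate .05 tests have no key outcome or combining rule

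*Combined protocol and SAP*

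**What the plan says.** All references are to the combined protocol and SAP.

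- **Hypothesis (10.1).** H1 reads "The HRVB program will show to be feasible and efficient in terms of increasing HRV and reducing stress, anxiety and/or depression". H0 is its negation.
- **Feasibility.** This is the primary question (3.2). Section 4.1 lists "the number of eligible patients, the rate of study participation acceptance and the rate of drop out", and 8.2.1 adds "compliance with study protocol (number and duration of sessions, fulfilling study questionnaires) and the ratio of drop out". For the analysis, 10.4 says "Acceptability of the study protocol and intervention as well as satisfaction will be reported descriptively". Sections 7.4 and 10.4.1 add descriptive use of drop-out data. The only threshold is the five 10-minute sessions in 6.3 and 7.2.1, which applies to one participant, not to the study.
- **Efficacy outcomes.** Section 4.2 lists "HRV (i.e., root-mean square differences of successive R-R intervals), perceived stress, and mental health (anxiety, depression, PTSD". Section 8.2.2 takes RMSSD (spelled RMSDD there) and adds "as well as High Frequency (HF) will be used as measures to assess HRV level before and after participation". Objective 3.3 names perceived stress and anxiety, 10.1 adds depression, and 4.2 also includes PTSD.
- **Efficacy tests (10.4).** Variables are compared "from baseline to post-HRVB intervention using non-parametric Kruskall-Wallis tests", and "By convention, statistical significance will be set at .05". Section 10.2 says the tests are one-tailed.
- **Design.** One open-label group with no comparator (2.5, 5.1, 7.1).

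**The concern.** A hypothesis should come with a rule that says which results support it. Here the feasible half has no such rule, because its measures are only described. The efficient half has several separate tests, and nothing says which of them must succeed. The investigators could settle after seeing the data whether HF may stand in for RMSSD, and so whether H1 is met.

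This matters because the results are meant to support a larger project (2.3) and a grant proposal (8.2.4). The test named in 10.4 adds a second problem. Kruskal-Wallis compares independent groups, whereas these are the same women measured twice, and it has no direction although 10.2 promises one-tailed tests.

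**Working it through.** **1. The plan's own figure.** Section 10.2 gives n=10 for effects above g=.81 with one-tailed tests, and states no numerical power. Assuming 80% power, a single paired test needs n = ((1.645 + 0.842)/0.81)² = 9.4, so 10. The exact one-sided paired t-test at n=10 has 76% power. The figure therefore fits one paired test with no drop-out.

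**2. What H1 asks for.** The sentence requires an HRV increase and a fall in stress, anxiety and/or depression. In ordinary usage *and/or* means at least one. What remains open is HRV: RMSSD alone (4.2), or either RMSSD or HF (8.2.2).

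Inputs: n=10; one-sided .05; paired t; d=.81 of the change-score SD on every outcome; three symptom scores. The .81 is the pre-post effect for stress and anxiety cited in 2.3. Applying it to HRV, and reading it on the change-score scale, are assumptions.

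With uncorrelated outcomes the arithmetic is direct, since each test has power .763:

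- at least one of three symptom scores: 1 − .237³ = .987
- RMSSD and at least one symptom: .763 × .987 = .753
- either index and at least one symptom: (1 − .237²) × .987 = .931

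Correlated cases were simulated with multivariate normal changes, 100,000 replicates per cell:

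| Assumed correlation | RMSSD alone | Either index |
|---|---|---|
| 0 between all outcomes | 75% | 93% |
| .5 between all outcomes | 74% | 86% |
| RMSSD–HF .8, symptoms .5, cross 0 to .3 | 72–73% | 80–81% |

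The undefined HRV rule is therefore worth about 12 to 18 percentage points, and about 8 if the two indices, taken from the same recording, correlate at .8.

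**3. The planned test.** Kruskal-Wallis scales the pre-post difference as if the two sets were independent. With a positive pre-post correlation the true variance is smaller, so the test is conservative and loses power. The documents do not say how a one-tailed result would be obtained from it, so two versions are shown: the signed root of H above 1.645, and the ordinary cut-off H > 3.84. Change-score d=.81, n=10, 100,000 replicates:

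| Assumed pre-post correlation | One-sided size (signed root) | Power, signed root | Power, ordinary cut-off |
|---|---|---|---|
| .3 | 3.1% | 67% | 52% |
| .5 | 1.6% | 55% | 37% |
| .7 | 0.6% | 34% | 18% |

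On the same basis the exact one-sided Wilcoxon signed-rank test has 71% power (true size 4.2%) and the paired t-test 76%, whatever the correlation.

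**4. Feasibility precision.** Exact two-sided 95% limits: 8/10 gives 44–97%, and 10/10 has a lower limit of .025^(1/10) = 69%. The one-sided 95% limit for 10/10 is .05^(1/10) = 74%. These apply only to measures with denominator 10, such as retention and reaching the minimum intervention. Acceptance has the mothers approached as its denominator, and eligible mothers per month is a count.

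**The case against.** The best reply is that the plan never runs 10.1 as a joint test. Objective 3.2 is to assess acceptability and satisfaction, 10.4 describes feasibility and confines inference to HRV and symptoms, and description is legitimate in a study of ten. On this view 10.1 is only loosely worded. That has force: the feasibility measures are sensible, and the missing progression thresholds alone would be missing detail. But the protocol chose to state H0/H1, claim appropriate power and set a .05 level, so hypothesis and analysis should agree.

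Four stronger readings are tempting, and the documents do not support them.

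- *H1 could require all three symptom scores.* Setting either index plus any symptom (86–93%) against RMSSD plus all three (34–49%) looks dramatic. But the strict reading drops the *or*, and the contrast moves two rules at once.
- *Many tests at .05 inflate the error rate.* Six independent tests would give 1 − .95⁶ = 26.5%. But H1 requires an HRV gain as well as a symptom gain, and the planned test is conservative. The loose decision rule is the main issue.
- *Ten women cannot test any feasibility criterion above 69%.* That limit is two-sided and applies only where the denominator is 10.
- *The Kruskal-Wallis power is a single known figure.* It depends on a one-tailed conversion that the plan does not state and on an assumed pre-post correlation.

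**Conclusion.** The point stands in limited form. As written, H1 cannot be decided: its feasibility half has no study-level criterion, and its efficacy half has no key outcome, no combining rule and no ruling on RMSSD against HF. On the natural at-least-one reading, the HRV choice moves the chance of meeting the efficacy part from about 74–75% to 86–93%, given n=10, d=.81 throughout and outcome correlation 0 to .5. The gap shrinks if RMSSD and HF are highly correlated.

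Separately, the unpaired, non-directional test costs power: 37–55% per outcome at a pre-post correlation of .5, against 71–76% for paired tests.

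Efficacy is a secondary objective, and a single-group pre-post comparison cannot establish it in any case. This should be corrected, but it does not undermine the study's descriptive feasibility aim.

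**What to change.** Amend 10.1 and 10.4.

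**(a) Feasibility.** Take it out of H0/H1 and state that it is estimated. Report, each with an exact 95% CI:

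- acceptance, among eligible mothers approached;
- retention, as the share of all enrolled who complete the post-intervention assessment;
- separately, the share of all enrolled who reach the protocol's own minimum intervention. Section 7.4 counts non-compliers as dropouts, so the two measures would otherwise overlap.

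Keep the other measures already listed. If progression criteria are to be used, fix them before enrolment.

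**(b) HRV and symptoms.** Choose one of two routes:

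- Name RMSSD and one symptom score from objective 3.3 (perceived stress or anxiety; if STAI, name state or trait) as key outcomes. Test both with a one-sided paired test, such as Wilcoxon signed-rank, in place of Kruskal-Wallis. Give the rest as estimates with CIs.
- Or label all HRV and symptom analyses exploratory, with paired estimates and CIs only.

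Under either route, call the result pre-post change, not efficacy.

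**Cost.** An amendment needing sponsor and ethics committee approval (1.3), with no new data or participants. Fewer results can be called significant. With two key outcomes at d=.81 and ten completers, power for both is about 51–57% (signed-rank) or 58–63% (paired t) at outcome correlation 0 to .5. Because 10.4.1 analyses completers only, the paired t figure falls to 51–57% with one drop-out and 44–50% with two. The exploratory route has no power cost, since it makes no significance claim.
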